5.2 Demographic and Baseline Characteristics

Demographic and baseline characteristics will be summarized. For quantitative variables, mean, SD, median, and minimum, and maximum will be provided. For qualitative variables, the frequency and percentage will be provided.

5.3 Safety Analysis

The safety analyses will be addressed by listing and tabulation of AEs (includes suspected ADRs), clinical laboratory tests including inhibitor (immunogenicity) and functional activity testing, thrombogenicity, vital signs, and physical examinations. Data will be described using descriptive analyses.

5.3.1 Adverse Events

Safety analysis will be primarily focused on a descriptive analysis of suspected ADRs. Safety assessment will be based on the prevalence of suspected ADRs that occurred during the clinical study.

Adverse events will be coded and classified using MedDRA terms (system organ class [SOC] and preferred term [PT]).

Adverse events will be classified as treatment-emergent AEs (TEAEs) or non-treatment-emergent AEs (non-TEAEs) depending on the comparison of AE onset date/time with the start date/time of study treatment after the subject joins the study. A TEAE will be defined as an AE which occurs between the beginning of the first infusion of study treatment after the subject joins the study and the final visit of the clinical study. A non-TEAE will be defined as an AE which occurs prior to the start of study treatment after the subject joins the study. Non-TEAEs and TEAEs will be summarized separately.

All AEs will be summarized by presenting subject incidences and percentages, and they will also be listed by subject and by SOC.

In addition, TEAEs, including suspected ADRs, will be summarized by SOC, PT, causal-relationship, intensity (severity) and seriousness (serious vs non-serious) using descriptive statistics. Each subject will only be counted once at each level of SOC or PT. For the summary by severity or causality, a subject will only be counted once per SOC or PT using the most severe AE or the AE with the strongest causal relationship to study treatment.

Adverse events temporally associated to the infusion of study treatment (ie, infusional AEs, including infusional suspected ADRs), will be summarized by presenting infusion/subject incidences and percentage and ordered by ordinal number of infusions, and listed. Temporally associated AEs occurring during study drug infusion or within 24 hours post the end of study drug infusion, and occurring during or within 72 hours post the end of study drug infusion will be summarized separately.

Subjects with a SAE or who withdraw from the study because of an AE will also be individually listed and summarized.

5.3.2 Clinical Laboratory Values Including Inhibitor (Immunogenicity) and Functional Activity Testing

All clinical laboratory data will be listed for each subject. The investigator will be required to classify out of the normal range laboratory results reported by the laboratory as clinically significant or not according to his/her criteria. Out of the normal range laboratory results judged by the investigator as clinically significant in the context of the subject's medical history will be considered AEs.

The presence and titer of FVIII and VWF inhibitors and functional activity testing results will be listed for each subject.

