1.2 Rationale

At the request of the Spanish Agency of Medicines and Medical Devices (AEMPS), Instituto Grifols, S.A is conducting a Phase 4, observational, multi-center, prospective, post-authorization cohort study examining the safety (including key safety parameters of inhibitor development [immunogenicity] and thrombogenicity) and clinical efficacy of long term use of Fanhdi in subjects with VWD according to the current guidelines (24). Data on the use of Fanhdi in routine clinical practice in the prophylaxis and/or treatment of subjects with VWD will be collected during an observation period of 12 months.

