2.1 Safety Objective

- To evaluate the safety (immunogenicity and thrombogenicity) associated with long term use of Fanhdi (see Sections 3.5.1.2 and 3.5.1.3)

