4.3.2 Suspected Adverse Drug Reactions

All noxious and unintended responses to a medicinal product or study treatment related to any dose should be considered suspected ADRs. The phrase “responses to a medicinal product” means that a causal relationship between a medicinal product or study treatment and an AE is at least a reasonable possibility.

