4.4 Assessment of Causality of Adverse Event

The investigator is required to provide a causality assessment for each AE reported to the sponsor. The sponsor will consider the investigator’s causality assessment and also provide its own assessment.

Causal relationship to the study drug will be established according to medical judgment on whether there is a **reasonable possibility of a causal relationship between the AE and the study drug administration.**

The investigator must determine and classify the AE causality according to the following categories:

Unrelated/Not related: there is not a reasonable possibility of causal relationship between the AE and the study drug.

Possibly related: there is evidence to suggest a causal relationship between the study drug and the AE.

Definitely related: there is a reason to conclude that the study drug caused the AE.

Criteria to assess the causal relationship should take into account of the following conditions:

1. A plausible temporal sequence from the study drug administration to the AE onset
2. Whether the event follows a known response pattern to the suspected treatment
3. Whether the AE could be reasonably explained by the subject's clinical state, comorbidities, or concomitant medications
4. The occurrence of improvement on stopping/reducing the treatment (positive dechallenge) and/or reappearance of the event on repeated exposure (positive rechallenge).

For expedited safety reporting purposes, AEs assessed as either “definitively related” or “possible related” will be considered POTENTIALLY RELATED or just RELATED.

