5.3.3 Thrombogenicity Assessment

Arterial and venous thromboembolic AEs, according to ICD-9-CM definitions, will be separately summarized. Temporally-associated events occurring during or within 72 hours post the end of study drug infusion will be separately presented.

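### Section 5.3.1 rests the safety assessment on suspected ADRs, which does not match the safety objective of immunogenicity and thrombogenicity

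*Protocol*

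**What the plan says.** Section 2.1 gives a single safety objective: "To evaluate the safety (immunogenicity and thrombogenicity) associated with long term use of Fanhdi". Section 1.2, which explains that a regulator asked for the study, describes safety as "including key safety parameters of inhibitor development [immunogenicity] and thrombogenicity".

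Section 5.3.1 opens with two sentences that set a different emphasis: "Safety analysis will be primarily focused on a descriptive analysis of suspected ADRs", followed by "Safety assessment will be based on the prevalence of suspected ADRs that occurred during the clinical study".

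Under Section 4.3.2 an event is a suspected ADR only if "a causal relationship between a medicinal product or study treatment and an AE is at least a reasonable possibility". Section 4.4 lists what to weigh in that judgement, including "Whether the AE could be reasonably explained by the subject's clinical state, comorbidities, or concomitant medications".

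For the two components of the objective, Section 5.3.3 states: "Arterial and venous thromboembolic AEs, according to ICD-9-CM definitions, will be separately summarized". It applies no causality restriction. Section 5.3.2 plans only a by-subject listing of inhibitor presence and titre, although Section 3.5.1.2 says that cumulative incidence by number of exposures will be collected.

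**The concern.** The objective asks whether subjects develop inhibitors or thromboembolic events. The sentence that says what the safety assessment rests on names another quantity, one that passes through a causality judgement on each event. In an uncontrolled cohort of about 15 subjects, judging single cases is a weak way to separate a drug effect from background. An event that belongs to the objective can therefore be missing from the stated basis of the safety conclusion.

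At stake is what the study report leads with. An SAP or report that follows Section 5.3.1 literally would draw its safety conclusion from the suspected-ADR count and treat the outcomes in the objective as side tables.

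**Working it through.** The protocol gives no safety figure to reproduce: the sample size was not formally calculated (Section 5.5), and no event rate, confidence level or threshold is stated. The check is mainly a comparison of sections.

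**Step 1. Does the stated basis cover thrombogenicity?** Sections 3.5.1.3 and 4.3.3 require every thromboembolic event to be recorded as an AE. Section 4.4 has the investigator classify each AE as unrelated, possibly related or definitely related. Unrelated means no reasonable possibility of causation, which is the complement of the suspected-ADR definition in Section 4.3.2. An unrelated thromboembolic event is therefore an AE but not a suspected ADR, and it does not enter the prevalence named in Section 5.3.1.

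**Step 2. Where would that event still be reported?** It would appear in the Section 5.3.3 thromboembolic summary, in the all-AE and treatment-emergent tables of Section 5.3.1 (if it began after the first infusion), and in the SAE listing if serious. It is reported, but outside the stated basis.

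**Step 3. Does the stated basis cover immunogenicity?** Under Section 5.3.2 an abnormal laboratory result becomes an AE only if the investigator judges it clinically significant. An inhibitor not so judged is not an AE, hence not a suspected ADR. Section 4.8 narrows this gap: a laboratory abnormality that leads to withdrawal is one of its examples of clinical significance, and Section 3.2.3 lists inhibitor development among the reasons for withdrawal. An inhibitor that leads to neither withdrawal nor a judgement of significance would be found only in the Section 5.3.2 listing. No summary of inhibitor incidence is stated.

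**Step 4. Illustration of the difference.** Assume 15 subjects, one of whom has a thromboembolic event judged unrelated, and no suspected ADR in anyone. Exact (Clopper-Pearson) 95% limits:

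- Suspected-ADR count: 0/15 = 0%. Upper limit = 1 − 0.025^(1/15) = 0.218. Interval 0 to 21.8%.
- Thromboembolic count: 1/15 = 6.7%. Lower limit = 1 − 0.975^(1/15) = 0.0017. The upper limit solves (1 − p)^15 + 15p(1 − p)^14 = 0.025, giving p = 0.319. Interval 0.2 to 31.9%.

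**Step 5. Denominators.** The Safety population is all enrolled subjects (Section 5.1). Events count as treatment-emergent only from the first infusion (Section 5.3.1), and inhibitor testing is at the investigator's discretion (Section 3.5.1.2). Dividing inhibitor cases by all enrolled subjects would count untested subjects as negative.

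**Step 6. Terminology.** Section 5.3.1 speaks of prevalence for suspected ADRs but reports AEs as subject incidences. New events over follow-up are an incidence.

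**The case against.** The strongest reply is that the two sentences sit in the adverse-event subsection and describe emphasis there. The parent Section 5.3 and the synopsis place AEs, inhibitor testing and thrombogenicity side by side and give suspected ADRs no priority. Section 3.3.1 lists five safety variables without ranking them. The study is descriptive. Every thromboembolic AE is tabulated regardless of causality, and those within 72 hours of an infusion are presented again.

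Most of this stands, and it limits the point. A reader might infer that the protocol has two competing primary safety outcomes. It does not, because no safety outcome is labelled primary. A reader might also infer that a suspected-ADR count decides the safety question and that an unrelated thromboembolic event disappears. There is no hypothesis, threshold or decision rule, and the event stays visible in several required outputs.

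The causality assessment is also less one-sided than the alternative-explanation criterion suggests. Section 4.4 lists temporal sequence, known response pattern, and dechallenge or rechallenge too, and the sponsor makes its own assessment. The documents do not say how often a thromboembolic event would be judged unrelated.

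What the reply does not remove is the wording. Both sentences speak of the safety analysis and safety assessment without limiting them to AE tables, and no other section says what the safety assessment rests on. Being tabulated is not the same as being the basis of the conclusion. The reply is weakest on inhibitors, which have a listing and no stated summary. Nor is this a detail left to the SAP, since the protocol itself states the basis and an SAP that follows it would carry the mismatch forward.

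**Conclusion.** The point holds as a mismatch between the Section 2.1 objective and the basis stated in Section 5.3.1. By the protocol's own definitions, that basis omits thromboembolic events judged unrelated and inhibitors not judged clinically significant. The first remain in the Section 5.3.3 and AE summaries; the second remain only in a listing.

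This is a modest correction of wording and alignment, with no consequence for sample size or error rates. The contrast of 0/15 with 1/15 is an illustration that rests on the assumed single event and on 15 subjects. The two intervals overlap widely, so it would be wrong to infer that the two counts give opposite answers on safety. No probability of such a case can be derived, because the protocol supplies neither a thromboembolic rate nor a share of events judged unrelated.

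**What to change.** Replace the two opening sentences of Section 5.3.1 with a statement that the safety conclusion rests on the Section 2.1 outcomes, and that suspected ADRs and other AEs are supportive:

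- (a) subjects with any arterial or venous thromboembolic AE from the first infusion, irrespective of causality, over subjects with at least one Fanhdi infusion;
- (b) subjects with a new FVIII or VWF inhibitor, over subjects with at least one inhibitor test after the first infusion, with the number never tested stated alongside.

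Report each as n/N with an exact 95% CI. In Section 5.3.2, summarise inhibitor incidence in addition to the listing. Use incidence in place of prevalence in Section 5.3.1. The general text of Section 5.3 and the synopsis need no replacement, since neither gives suspected ADRs priority.

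The cost is a few sentences and two summary rows from data the protocol already plans to collect. The downside is that the headline safety figure may look slightly less favourable, because events judged unrelated are counted. The inhibitor figure may also rest on fewer subjects than were enrolled, which the count of untested subjects makes visible.

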4.2 Adverse Event Monitoring

Subjects must be carefully monitored for AEs. This monitoring includes clinical and laboratory tests and physical signs; any abnormalities judged by the investigator as clinically significant will be considered AEs. See [Section 4.3](#) for AE definitions. Adverse events should be assessed in terms of their seriousness, severity, and causal relationship to study treatment.

Adverse events will be elicited by spontaneous reporting by the study individual or by a non-leading inquiry or direct observation by the study staff.

All study subjects will be monitored after an AE until it is resolved. This monitoring includes clinical and laboratory tests and vital signs.

Adverse events and SAEs must be documented from signing of the ICF until the subject completes his or her final study visit, whether the subject completes the study or suspends participation early for any reason.

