4.8 Adverse Event Documentation

All AEs and SAEs occurring after the subject has **signed the ICF through the final study visit** (ie, last day of the subject’s participation in the clinical study, whether the subject completes the study or participation is suspended early for any reason) must be fully recorded

in the subject's eCRF, source documents, and SAE report form (if serious) as well as in the medical record. If no AE has occurred during the study period, this should also be indicated in the eCRF.

It is the responsibility of the investigator to ensure that all AEs (either serious or non-serious) are appropriately recorded in the eCRF and subject's source documents in a timely manner (up to 5 calendar days upon being made aware of AE occurrence).

At each visit, AEs will be elicited by asking the individual a non-leading question such as "Do you feel different in any way since the last visit?" Moreover, AEs will also be collected through directly observed events or spontaneously volunteered by the subject. Clearly related signs, symptoms and abnormal diagnostic procedures should preferably be grouped together and recorded as a single diagnosis or syndrome wherever possible.

The following variables must be recorded in the AE eCRF and source documents:

- The verbatim term (a diagnosis is preferred)
- Date/time of onset
- Date/time of resolution
- Severity (mild, moderate, severe)
- Causality (unrelated, possibly related, definitely related)*
- Seriousness (yes, no)
- Action taken (with regard to study treatment)
- Other action (to treat the event)
- Outcome and sequel (follow-up on AE)

*Causality assessment will be made only when the AE occurs after the subject has initiated at least one infusion of the study drug. An AE occurring before subject's exposure to study treatment will be always labeled as "unrelated/not related".

For AEs that occur during infusions, the time of onset of the AE, and the time of AE change materially in intensity (recorded as a separate AE), and/or resolve will be captured in the eCRF.

In addition to the investigator's own description of the AEs, each AE will be encoded according to the Medical Dictionary for Regulatory Activities (MedDRA®).

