5.3.5 Physical Examinations

Physical examination findings (normal and abnormal) will be listed for each subject. Any clinically significant abnormality developed during the clinical study and not already present at screening will be reported and analyzed as an AE.

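### TEAE status rests on onset time alone, and outside infusions nothing requires a worsened pre-infusion AE to be re-recorded, so such worsening can miss the TEAE and suspected-ADR summaries

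*Protocol*

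**What the plan says.** Protocol Section 5.3.1 assigns each AE to one of two classes "depending on the comparison of AE onset date/time with the start date/time of study treatment after the subject joins the study". The first class is defined thus: "A TEAE will be defined as an AE which occurs between the beginning of the first infusion of study treatment" and the final visit. The second: "A non-TEAE will be defined as an AE which occurs prior to the start of study treatment after the subject joins the study". The two classes are summarized separately. Only TEAEs go on to the tables by system organ class, preferred term, causality, severity and seriousness. The same section makes suspected ADRs the main focus of the safety analysis.

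AEs that precede treatment are in the database by design. Section 4.2 states: "Adverse events and SAEs must be documented from signing of the ICF until the subject completes his or her final study visit".

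Section 4.8 contains the only rule that gives a change in severity its own record. Its scope is set by its opening words, "For AEs that occur during infusions, the time of onset of the AE", and it goes on to "the time of AE change materially in intensity (recorded as a separate AE". A footnote in the same section restricts causality assessment to AEs that occur once at least one infusion has been started. An AE that precedes "exposure to study treatment will be always labeled as" unrelated.

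**The concern.** A treatment-emergent flag should pick up what happens under treatment. That includes an event already present at the first dose that then becomes worse. The protocol's definition looks only at when the event began.

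That could be harmless if sites had to open a new record whenever an AE worsened, because the new record would carry a post-infusion onset. Section 4.8 requires this only for AEs during infusions.

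Two outputs are at stake. One is the set of TEAE tables. The other is the suspected-ADR summary, because a record labeled unrelated by rule cannot meet the definition in Section 4.3.2, which needs at least a reasonable possibility of a causal link.

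**Working it through.** The protocol gives no figure on this point to reproduce, so the check applies the written rules case by case.

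**Inputs**
- Classification criterion: onset date/time against the start of the first on-study infusion (5.3.1).
- Collection window: from consent to the final visit (3.5.1.1, 4.2, 4.8).
- Separate-record rule: a material change in intensity, for AEs during infusions (4.8).
- Causality of pre-exposure AEs: fixed as unrelated (4.8).
- Planned size: about 15 subjects, not formally calculated (5.5).

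**Cases**

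| Case | Onset | Later course | Record required by 4.8 | Class under 5.3.1 |
|---|---|---|---|---|
| a | After start of first infusion | Any | Original | TEAE |
| b | Between consent and first infusion | No change | Original | Non-TEAE |
| c | Between consent and first infusion | Worsens after first infusion, not during an infusion | Original only | Non-TEAE, causality fixed as unrelated |
| d | Between consent and first infusion | Material change during an infusion | Separate AE, if 4.8 is read broadly | TEAE |

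Case c is the gap. Case d depends on reading 4.8 to cover any AE present during an infusion. If it covers only AEs that begin during one, case d joins case c and the gap is wider.

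**Is there a worsening rule elsewhere?** Sections 3.5.1.1, 4.2 to 4.4, 4.7 to 4.8 and 5.3.1 to 5.3.5 contain none that sends a worsened AE to a new record or to the TEAE class. Section 5.3.5 is also framed by first appearance: a clinically significant physical finding that developed during the study and was "not already present at screening will be reported and analyzed as an AE". It does not mention worsening of a finding already there.

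**Do the analysis windows help?** Section 5.3.1 summarizes AEs temporally associated with infusion, up to 24 and up to 72 hours after its end. A case c worsening two hours after an infusion falls inside both windows. Its single record keeps a pre-treatment onset, so it may be left out of these summaries too.

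**Can case c arise?** It needs an interval between consent and first infusion. Inclusion criterion 3 (3.2.1) admits subjects who only expect a future bleed or procedure, and the observation period starts with the first infusion (3.1), so the interval can be long for them.

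**Scale.** One subject moved between classes changes a subject incidence by 1/15 = 0.067, or 6.7 percentage points. This holds for a given preferred term. It holds for overall TEAE incidence only if that subject has no other TEAE, because each subject is counted once per level.

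**The case against.** The strongest reply is that little is lost and little depends on it. The study is a descriptive single cohort with no hypothesis test, and no decision threshold uses the TEAE count. All AEs are summarized and listed, non-TEAEs have their own summary, and subjects with an SAE or an AE leading to withdrawal are listed whatever their TEAE status. The named safety topics have their own outputs: inhibitor results are listed by subject (5.3.2) and thromboembolic AEs are summarized separately (5.3.3). All of this stands. A reader might infer that such events vanish from the safety report; they do not. They are put in the wrong class.

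A reader might also infer that a worsened AE can never become treatment-emergent. The protocol does not support that. The AE definition in 4.3.1 is broad, nothing forbids an investigator from opening a new record, and clinically significant laboratory and vital-sign abnormalities are AEs in their own right (3.5.1.4, 4.8, 5.3.2, 5.3.4). What holds is narrower: outside infusions, re-recording is not required.

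Subjects enrolled with active bleeding might seem the obvious example. They are not. That bleed began before inclusion, bleeds are collected as efficacy events with their own severity data (3.5.2.1), and these subjects are likely to be infused promptly.

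Finally, Section 5 leaves data handling to the statistical analysis plan, which is not at hand and could add rules. That answers only part of the point. The protocol itself fixes the TEAE definition, and no analysis plan can recover a change in intensity that sites did not record. Section 4.4 does have the sponsor make its own causality assessment, but the label in 4.8 allows no exception.

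**Conclusion.** The point holds as a modest defect in a stated rule. An AE that starts between consent and first infusion and worsens afterwards, outside an infusion, need not be re-recorded. If it is not, it stays a non-TEAE and cannot be a suspected ADR, while remaining visible in the all-AE, non-TEAE and, if serious, SAE outputs.

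The conclusion rests on the plain reading of 5.3.1 and 4.8, and on sites doing no more than 4.8 asks. It applies mainly to subjects who consent while waiting for a future bleed or procedure.

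The expected number of such events is small and cannot be estimated from the protocol. A reader might infer a count by assuming, say, that 10% to 30% of subjects have an AE ongoing at first infusion and that 20% to 30% of those worsen. That gives 15 × 0.10 × 0.20 = 0.30 to 15 × 0.30 × 0.30 = 1.35 subjects. The protocol contains none of these rates, so the range is illustrative only. The firm figure is 6.7 percentage points per subject for a given preferred term.

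**What to change.** Three short changes to the protocol:

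1. In 5.3.1, define a TEAE as an AE that starts on or after the beginning of the first on-study infusion, or that started earlier and increases in severity or becomes serious on or after that time. Adjust the non-TEAE definition to match.
2. In 4.8, apply the separate-record rule to any material increase in intensity after the first infusion, whether or not an infusion is running.
3. In the causality footnote of 4.8, allow causality to be assessed for that worsened record. The original pre-exposure record can keep its label.

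The cost is two or three sentences, one added eCRF instruction, a few more AE records and a slightly higher TEAE count. Treatment and the analysis population are unaffected. The second and third changes need to be in place while data are being collected, because they govern what sites record.
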